#### **14.3. Determination of Severity**

The severity of AEs will be assessed according to the Common Terminology Criteria for Adverse Events (CTCAE), Version 4.03. If the AE is not defined in the CTCAE, the investigator will determine the severity based on the following definitions from the CTCAE:

- Grade 1 (Mild): Asymptomatic or mild symptoms, clinical or diagnostic observations only with no intervention indicated
- Grade 2 (Moderate): Minimal, local or noninvasive intervention indicated, limiting instrumental ADL
- Grade 3 (Severe): Medically significant but not immediately life-threatening, causing hospitalization or prolongation of hospitalization, disabling and limiting self-care AL
- Grade 4 (Life-Threatening): Urgent intervention indicated
- Grade 5 (Death)

#### **14.4. Adverse Event Reporting**

AROG has standards for reporting AEs that are to be followed regardless of applicable regulatory requirements that may be less stringent. Lack of drug effect is not an AE in clinical trials, because the purpose of the clinical trial is to establish drug effect.

Adverse Events (AEs) will be evaluated according to CTCAE version 4.03 and documented in medical record. After the Informed Consent Document (ICD) is signed, study site personnel will record the occurrence and nature of each patient's pre-existing conditions, including clinically significant signs and symptoms of the disease. During the study, site personnel will record any change in the pre-existing condition(s) and the occurrence and nature of any new adverse events.

All AEs related to protocol procedures are reported to AROG or designee. All AEs occurring after the patient receives the first dose of study drug must be reported to AROG or its designee via CRF. Investigators will be instructed to report to AROG or its designee their assessment of the potential relatedness of each AE to protocol procedure, studied disease state, study drug, and/or drug delivery system via CRF.

For all AEs, the investigator should specify:

1. ***Seriousness:*** Seriousness of an AE is defined by the criteria described in Section 10.1. A severe AE should not always be considered as serious.
2. ***Date of onset and its duration (start and end dates):*** The investigator should follow up the outcome of any AEs until they return to normal or consolidation of the subject's condition. All adverse events still evolving at the end of the study are to be followed up by the investigator until their resolution or stabilization.
3. ***Severity:*** (using NCI CTCAE v.4.03),

4. **Action taken with respect to study drug:** (no action taken; study drug dosage adjusted/temporarily interrupted; study drug permanently discontinued due to this adverse event; hospitalization/prolonged hospitalization), corrective treatment/therapy given, additional investigations performed
5. **Outcome:** Resolved/Recovered, recovering/resolving, not recovered/resolved, recovered/resolved with sequelae, unknown
6. **Relatedness:** If an AE is related or not related to study drug

### **Follow-up of unresolved adverse events**

Any AEs that are unresolved at the subject's last visit in the study are to be followed up by the investigator for as long as medically indicated. The sponsor retains the right to request additional information for any subject with ongoing AE(s) at the end of the study, if judged necessary.

### *CASE OF ROUTINE LABORATORY MEASUREMENTS*

A value outside the normal or reference range in a routine safety assessment, such as clinical laboratory may be considered as an AE. However, laboratory, as well as vital signs abnormalities, are to be recorded into the eCRF as AEs only if they are considered medically relevant by the investigator: i.e. symptomatic, requiring corrective treatment, leading to IMP discontinuation/dose modification (reduction and/or delay), and/or fulfilling a seriousness criterion. Deterioration of a laboratory value that is unequivocally due to disease progression should not be reported as an AE. If the findings contribute to a clinical diagnosis (such as hepatitis in case of increased liver enzymes) this diagnosis should be recorded as an adverse event.

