#### **8.4.2. Dose Reductions of Crenolanib for Hematologic Toxicities**

Subjects with neutropenia or thrombocytopenia as a consequence of the disease or chemotherapy do not require treatment interruptions for myelosuppression. Drug hold or dose reduction in these subjects may be considered in an individual case and should be discussed with the medical monitor at AROG prior to the drug hold. All dose holds and reductions should be captured in CRFs. Dose re-escalation is not allowed on this protocol, any exception must be approved by the sponsor in writing.

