### **13.8. Safety Analyses**

All subjects will be evaluable for safety. Adverse events that occur after a subject is entered (signs informed consent), but before the patient receives study drug, will not be recorded on the CRF unless the investigator believes that the events may have been caused by a protocol procedure. Safety analyses will include summaries of the incidence of adverse events by maximum CTCAE

grade (version 4.03; NCI 2010) that occur during the study treatment period or within 30 days of the last dose of study treatment or until alternate therapy is started, regardless of causality or relatedness to study drug. The safety-related outcomes that will be summarized include:

- Adverse events,
- TEAEs,
- SAEs,
- Deaths,
- Discontinuations due to adverse events,
- Extent of exposure to study drug treatment,
- Hospitalizations,
- Use of key concomitant medications.

Analyses for data with discrete dates (for example, death date and start/stop dates of concomitant medications) will be performed through 30 days after the patient has been discontinued from study treatment or until alternate therapy is started. Adverse events will also be analyzed in this time frame. After 30-day post-discontinuation follow-up, only those SAEs that are thought to be related to study treatment or protocol procedure should be reported immediately to AROG or its designee. For these events, the patient must be followed until the event has resolved or stabilized.

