## 14. SAFETY EVALUATIONS AND APPROPRIATENESS OF MEASUREMENTS

### 14.1. Definitions of Adverse Events

#### 14.1.1. Adverse Event (AE)

Any harm or untoward medical occurrence in a research participant administered a medical product, medical treatment or procedure even if it does not necessarily have a causal relationship with the product, treatment, or procedure. An adverse event can be any unfavorable and unintended sign (including an abnormal laboratory finding, for example), symptom, or disease temporally associated with the use of a medical product, medical treatment, or procedure whether or not considered to be related. All adverse events regardless of grade must be recorded, graded, and reported to the Sponsor.

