**Key:**

a count recovery is defined as : ANC  $\geq$ 1000 and platelets  $\geq$ 100,000

a Screening assessments should be performed within 28 days of enrollment with the following exceptions: CBC, CMP and pregnancy test (when applicable) should be performed within 7 days of enrollment, bone marrow biopsy and aspirate and evaluation of FLT3 and other mutational status should be performed within 21 days of enrollment

\* If screening assessments were performed while patient was receiving induction chemotherapy, the following assessments performed prior to starting induction, if done per standard of care, may be requested by the sponsor: CBC with differential, CMP with bilirubin, ALT/AST, and bone marrow biopsy and aspiration

b EKG is to be performed pre-dose crenolanib (baseline on the first day of crenolanib) as well as 2 hours ( $\pm$  30 minutes) post first dose of crenolanib during Induction 1

c Peripheral and whole blood samples for translation research (including PK analysis) should be collected as defined in Section 11.

\*\* EKG, Peripheral blood for PK analysis and Whole blood sample will only be collected during Induction 1

d CBC with differential and CMP should be performed at least weekly while patients are receiving crenolanib during induction. Additional labs may be performed per SOC, for safety, the sponsor may request additional labs done per SOC be captured

e Bone marrow biopsy and aspirate performed on day 14-28 should have FLT3 testing and mutational status if available

Per SOC: Physician visits (with ECOG PS, vitals, weight, concomitant medication assessment and adverse events assessments) should be performed as per SOC while patients are receiving crenolanib during induction. At a minimum adverse events and concomitant medications should be reported to the sponsor (per EDC) monthly.

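### Two different rules decide when a laboratory abnormality is recorded as an AE, and Section 13.8 names no analysis of the measured values that would make the difference harmless

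*Combined protocol and SAP*

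**What the plan says.** **Recording.** Section 14.1.1 states: "An adverse event can be any unfavorable and unintended sign (including an abnormal laboratory finding, for example), symptom, or disease". It adds: "All adverse events regardless of grade must be recorded, graded, and reported to the Sponsor". The subsection of 14.4 on routine laboratory measurements is narrower. Laboratory and vital-sign "abnormalities, are to be recorded into the eCRF as AEs only if they are considered medically relevant by the investigator". It explains medical relevance as being symptomatic, needing corrective treatment, "leading to IMP discontinuation/dose modification (reduction and/or delay), and/or fulfilling a seriousness criterion". It also keeps out laboratory deterioration that is unequivocally due to disease progression.

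**Analysis.** Section 13.8 says: "Safety analyses will include summaries of the incidence of adverse events by maximum CTCAE" grade. Its list, introduced by "The safety-related outcomes that will be summarized include", covers AEs, TEAEs, SAEs, deaths, discontinuations due to AEs, exposure, hospitalizations and key concomitant medications. It names no laboratory values, grades derived from them or shifts from baseline.

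**Measurement.** The Appendix IV induction key states: "CBC with differential and CMP should be performed at least weekly while patients are receiving crenolanib during induction". Section 10.3 sets at least weekly tests in consolidation and Day 1 of each cycle in maintenance.

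**Drug action.** Tables 6 and 7 continue the current dose at Grade 1 and stop crenolanib at Grade 2 or higher elevation of bilirubin, ALT, AST or alkaline phosphatase. Section 8.4.2 says that patients with neutropenia or thrombocytopenia caused by disease or chemotherapy "do not require treatment interruptions for myelosuppression".

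**The concern.** Safety and tolerability is the first-listed primary objective. Hepatic dysfunction heads the list of expected crenolanib toxicities in Section 13.2.2, and Section 5.2 offers less myelosuppression only as a possibility. Laboratory data bear on both.

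If recorded AEs are the route by which laboratory toxicity reaches the tables, the reported rates mix what happened to patients with how each site read the recording rule. Two sites that both follow the protocol could report different numerators from identical laboratory results. The narrower rule can only lower the count, so any bias is toward a cleaner profile.

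**Working it through.** The plan states no laboratory-toxicity rate, so there is no figure of that kind to reproduce. The check sets the rules side by side, then illustrates the size.

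**Step 1. Which findings the two rules treat differently.** The middle column takes the finding to be an AE under 14.1.1.

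| Finding | 14.1.1 | 14.4 |
|---|---|---|
| Grade 1 ALT/AST (up to 3.0 x ULN) or bilirubin (up to 1.5 x ULN), asymptomatic, untreated, on drug | Recorded | Not recorded: Tables 6 and 7 leave the dose unchanged |
| Grade 2 or higher liver elevation, attributed to crenolanib, on drug | Recorded | Recorded: the stop meets the dose-change criterion |
| Liver elevation attributed to chemotherapy or disease | Recorded | Depends: Section 8.4.1 frames the reductions for toxicity attributed to crenolanib, and the tables are headed as recommendations |
| Liver elevation while crenolanib is held | Recorded | Only if symptomatic, treated or serious, or if it delays a restart |
| Cytopenia from disease or chemotherapy, asymptomatic, untreated | Recorded | Not recorded unless serious or the dose is changed: Section 8.4.2 requires no interruption |
| Cytopenia needing corrective treatment | Recorded | Recorded |

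The rules agree in the second and last rows and can differ in the other four.

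**Step 2. Why a baseline shift is needed.** Sections 8.2.1 and 10.2 allow crenolanib to start with ALT and AST up to 2.0 x ULN. Appendix V puts Grade 1 from above ULN to 3.0 x ULN. A patient can therefore be Grade 1 before the first dose, and a recorded grade alone does not show worsening on drug. Section 14.6 keeps only the highest grade per cycle, and Section 8.3 lets a cycle exceed 28 days.

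**Step 3. Illustrative size for the exposed events.** Inputs: N = 120 (Section 13.1.2); the true rate t and the share of cases recorded c are assumptions.

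Reported rate = t x c. Half-width at full recording = 1.96 x sqrt(t(1 - t)/120).

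| t | c = 100% | 75% | 50% | 25% | Half-width |
|---|---|---|---|---|---|
| 30% | 30% (36 patients) | 22.5% (27) | 15% (18) | 7.5% (9) | 8.2 points |
| 20% | 20% (24) | 15% (18) | 10% (12) | 5% (6) | 7.2 points |

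For t = 30%: 1.96 x sqrt(0.30 x 0.70/120) = 0.082. At c = 50% the shortfall is 15 points against 8.2; for t = 20% it is 10 against 7.2. At c = 75% the shortfalls are 7.5 and 5 points, inside the half-widths.

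**Step 4. Whether the Grade 4 halting rule is exposed.** Section 13.2.2 halts at 2 of 6 or 3 of 12. The cut-offs reproduce: 1/6 = 16.7% and 2/12 = 16.7% do not exceed 20%, while 2/6 = 33.3% and 3/12 = 25% do. With X the events in the first 6 patients and Y those in the next 6, each with recorded rate p:

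P(halt by patient 12) = 1 - [P(X=0) x P(Y≤2) + P(X=1) x P(Y≤1)].

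At p = 0.20: 1 - (0.2621 x 0.9011 + 0.3932 x 0.6554) = 0.506. If only 75% or 50% of events were recorded (p = 0.15 or 0.10), this would fall to 0.331 or 0.163. For liver values those losses are not expected. The rule counts crenolanib-related Grade 4 events, and Tables 6 and 7 call for a stop at Grade 2 or higher, which brings such events into the AE data under either recording rule.

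**The case against.** The strongest reply is that the rules do not conflict: 14.1.1 says what an AE can be, 14.4 gives the specific test for laboratory values, and the all-grades requirement covers whatever passes it. That is a reasonable reading, but the text does not say that 14.4 governs, and a site applying 14.1.1 literally is also compliant. Adopting this reading would remove the inconsistency between sites. It would leave the investigator filter as the route into the named analyses.

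Several further objections stand and limit the point.

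- A reader might infer that hepatic toxicity rests wholly on site discretion. It does not. On-drug Grade 2 or higher elevations attributed to crenolanib normally qualify through the stop. Some Grade 1 values qualify too, because ALT or AST above 2.0 x ULN, or raised bilirubin, delays crenolanib in a later course and delay is a 14.4 criterion. A diagnosis such as hepatitis must also be recorded.
- A reader might infer that slow marrow recovery appears nowhere. The primary objective includes separate CR and CRi rates, and Section 12.1 separates them at neutrophils of 1.0 x 10^9/L and platelets of 100 x 10^9/L, the same thresholds as count recovery in Appendix IV. The CRi rate therefore partly reflects incomplete recovery, though only in responders and without the time taken. Treated cytopenia qualifies under 14.4.
- A reader might infer that AEs are the only laboratory route. The 13.8 list is introduced as inclusive, Section 13.1.1 plans descriptive summaries of continuous data without naming laboratory tests, and Section 13.1 announces a separate SAP that is not among the documents. That SAP could supply the tables, but it would not settle which recording rule sites apply.
- Weekly measurement does not extend to maintenance.
- In a single-arm trial, delayed recovery after 7+3 cannot be attributed to crenolanib without an outside comparison. A competing-risk analysis of recovery with committee reporting is a preference, not a correction.

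**Conclusion.** The point holds in a limited form. Sections 14.1.1 and 14.4 give different recording rules, neither is stated to govern, and Section 13.8 names no analysis of the measured values. The affected rates are those of asymptomatic Grade 1 liver elevations, of liver elevations attributed to chemotherapy or disease or arising while crenolanib is held, and of untreated asymptomatic cytopenias.

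The size cannot be fixed from the documents. The 15-point and 10-point shortfalls assume true rates of 30% and 20% and half of cases recorded. With three quarters recorded, the shortfall stays within sampling error. A firm figure for differences between sites might be inferred, but the documents give no Grade 1 frequency to support one.

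Nor do the documents support a claim that the Grade 4 halting rule is compromised. What is at stake is the completeness and comparability of the descriptive safety profile, not a decision rule. The change is still worth making, because safety is a primary objective and the better method uses data already required.

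**What to change.** 1. Reconcile Sections 14.1.1 and 14.4 to a single rule for recording laboratory abnormalities as AEs, with a cross-reference stating that it governs.
2. In Section 13.8, add worst post-baseline CTCAE 4.03 grade and shift from the pre-crenolanib baseline for ALT, AST, bilirubin, ANC and platelets. Derive both by program from the collected values (at least weekly in induction and consolidation, Day 1 of each maintenance cycle), and present them by phase and anthracycline.
3. Optional: a descriptive time to count recovery using the Appendix IV definition. The baseline CBC follows chemotherapy, so for counts this can be more informative than worst grade.

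The cost is a small amount of programming and a short protocol edit, with no new data. Reported any-grade laboratory toxicity rates may look less favourable than AE-based rates.

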### **14.5. Serious Adverse Event Reporting**

Serious adverse event collection begins after the patient has signed informed consent and has received a tablet or more of study drug. If a patient experiences an SAE after signing informed consent, but prior to receiving study drug, the event will NOT be collected unless the investigator feels the event may have been caused by a protocol procedure.

In case of a SAE, the investigator, within 24 hours of learning of the SAE or subject death, must notify the sponsor (Arog Pharmaceuticals by e-mail: [contact] or [contact]) and transmit the following information (within a signed SAE report form):

- Subject identification code, demographics and vitals
- Description of event with onset and duration (with CTCAE event term & severity)
- Dates, dose and frequency of study drug administered
- Assessment of the seriousness and causality of the event with the study drug using the causality criteria (EVCTM): related versus not related
- Study drug status (dose interrupted or discontinued)
- Date of death (if applicable)
- Concomitant therapy and interventions
- Pertinent laboratory data/diagnostic tests
- Pertinent medical history including underlying diagnosis

All SAEs must be followed by the investigator until resolution or stabilization until the subject's death. This may mean that follow-up will be extended beyond the subject's withdrawal from the trial. The investigator must provide follow-up information (outcome, more precise medical details, results of investigations, copy of discharge summary, etc...) within 24 hours of information becoming available to Arog Pharmaceuticals and to the study monitor, again using the SAE Report Form indicating follow-up. When this information is passed on, care must be taken to continue to respect subject anonymity. The study monitor may contact, or visit the investigator, in order to obtain details of the event.

The sponsor will report all SUSAR to the country specific regulatory authorities within the request period. The evaluation of expectedness is based on knowledge of the adverse reaction on the reference document: the current reference document is the latest version of the Investigator's Brochure of crenolanib.

The sponsor will also inform the IRB of any SAE with the potential to modify the benefit/risk ratio of the present study. The sponsor will be responsible for reporting of New Safety Issues and Annual Safety Reports to IRBs.

The following events **are not** to be considered as a SAE:

- Any event requiring short consultation in a hospital
- An external treatment in a hospital emergency service
- Any event clearly related to disease progression
  - Disease progression can be considered as a worsening of a patient's condition attributable to the disease for which the investigational product is being studied. It may be an increase in the severity of the disease under study and/or increases in the symptoms of the disease. The development of new, or progression of existing metastasis to the primary cancer under study should be considered as disease progression and not an AE or SAE. Events that are unequivocally due to disease progression should not be reported as AEs or SAEs during the study.
- Hospitalization (1 night or more) or hospitalization prolongation for one of the following reasons:
  - Planned hospitalization for routine intervention
  - Hospitalization or intervention requested by the protocol
  - Hospitalization for explorations not related to a modification of the subject's health
  - Hospitalization for comfort or for social reasons (for example: hospitalization of an elderly person due to dependence on his partner who was hospitalized)
  - Hospitalization not related to a subject's health worsening and not related to the study objectives (for example: plastic surgery)

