**Figure 7 Representative PIA analysis of patient plasma samples after taking crenolanib single agent.**

The study by Robert J. et al. in 16 leukemia patients showed that the major metabolites of idarubicin or daunorubicin were the 13-dihydroderivative of each drug, idarubicinol or daunorubicinol. The elimination half-life of idarubicinol was two times higher than that of daunorubicinol (80.7 h versus 37.3 h). [6] During 7+3 induction in this protocol, idarubicin or daunorubicin will be administered on days 1, 2, and 3. By the time crenolanib is started (Day 9), idarubicinol level should have declined by 75% (2 half-lives) and daunorubicinol levels will have dropped by 93.5% (4 half-lives). Crenolanib will be discontinued 3 days (9 half-lives) prior to initiation of subsequent chemotherapy.

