### **8.3. Treatment with Crenolanib (AR-868,596)**

The investigator or his/her designee is responsible for explaining the correct use of the investigational agent(s) to the subject or other site personnel such as inpatient staff, verifying that instructions are followed properly, maintaining accurate records of study drug dispensing and collection, and returning all unused and unopened medication to AROG or its designee at the end of the study. Study medication that has been dispensed but remains unused at the end of each cycle is recorded by the site personnel and either safely discarded if opened or returned to AROG if unopened with intact packaging.

Subjects will be instructed to contact the investigator as soon as possible if they have a complaint or problem with the study drug so that the situation can be handled.

**Missed Doses/Counting Cycle Days:** If a subject vomits after drug ingestion, no replacement dose is to be taken; the subject can continue to take the remaining doses as planned. If drug is held or a dose is missed by more than 3 hours after the scheduled time, the missed/held dose should not be made up. Dosing will resume with the next scheduled dose. The subject/nursing or research staff should enter in the diary the doses as missed and reason for missed dose. If drug is held or missed for a day or more, treatment should continue as if uninterrupted. As pill count for compliance assessment will be performed at each patient follow up; leftover drug should be returned to the study site by the subject upon follow up.

During induction and consolidation, one cycle is defined by start of chemotherapy and will continue until the start of next chemotherapy (i.e. induction 1 = cycle 1 and may exceed 28 days)

regardless whether drug is held. During maintenance, cycles will be 28 days in maximum duration (28 days = 1 cycle = 1 month).

“Days” of a cycle are to be counted sequentially from start of chemotherapy (not study drug) until start of next chemotherapy cycle. During maintenance, the start of a cycle is denoted by ingestion of the first dose of crenolanib after evaluation of efficacy at the end of induction or consolidation. The scheduled procedures/visits should comply with the study calendar regardless of amount of study drug administered.

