**13.2.1. Excessive early mortality**

Early stopping rules for excessive mortality will be applied in the safety phase of the study. Early mortality is defined for this study as death due to any cause within 30 and 60 days of the initiation of study treatment. In the VALOR trial, all-cause mortality rates of 7.9% and 19.7% were reported, respectively, for patients with relapsed/refractory AML who received cytarabine and placebo as induction therapy. [14] The 30-day mortality rate of 7.9% from the VALOR trial is similar to the 28-day mortality rate of 10.3% that was reported from a retrospective analysis of more than 3000 patients with newly diagnosed AML, the majority of whom were treated with cytarabine-based regimens as induction therapy.[11]

Based on the above considerations, enrollment in a cohort will be halted if the observed 30- and 60-day early mortality rate exceeds 10% and 20%, respectively, as follows: if 1 or more of the first 6 patients enrolled within a cohort die prior to Day 30 then enrollment of additional patients within that cohort will be halted pending review by the Protocol Safety Committee. Additionally, enrollment will be halted within a cohort if 2 or more of the patients die prior to Day 60. Otherwise, 6 additional patients will be enrolled within the cohort provided none of the other stopping criteria have been met.

For the second group of 6 patients within a cohort, if 2 or more of the patients enrolled within a cohort die prior to Day 30, then enrollment of additional patients will be halted pending review by the Protocol Safety Committee. Similarly, if 3 or more of the patients enrolled within a cohort die

prior to Day 60, then enrollment of additional patients will be halted for that cohort. If these and the other early stopping criteria are not met, then the 12 additional patients will be enrolled within the cohort.

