#### **14.8. Deaths**

All deaths that occur during the study should be reported as follows:

- Death, which is unequivocally due to disease progression, should be communicated to the study monitor at the next monitoring visit and should be documented in the CRF module, but should not be reported as a SAE during the study
- Where death is not clearly due to disease progression of the disease under study the AE causing the death should be reported to the study monitor as an SAE within 24 hours of becoming aware of the event. The report should contain a comment regarding the co-

involvement of progression of disease, if appropriate, and should assign a single primary cause of death together with any contributory causes

- Deaths with an unknown cause should always be reported as a SAE (within 24 hours of becoming aware of the event) but every effort should be made to establish a cause of death. A post-mortem may be helpful in the assessment of the cause of death, and if performed, a copy of the post-mortem results (with translation of important parts into English) should be reported in an expedited fashion to the sponsor within the usual timeframes

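### The reporting sections do not give the safety-phase mortality halting rule a consistent or timely count of deaths

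*Combined protocol and SAP*

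**What the plan says.** Section 13.2.1 sets the endpoint: "Early mortality is defined for this study as death due to any cause within 30 and 60 days of the initiation of study treatment". The rule is that "enrollment in a cohort will be halted if the observed 30- and 60-day early mortality rate exceeds 10% and 20%, respectively". It turns these rates into counts. For the first 6 patients of a cohort the trigger is 1 death before Day 30 or 2 before Day 60. With the second 6 enrolled it is 2 deaths before Day 30 or 3 before Day 60, which I read as cumulative counts out of 12.

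The initiation of study treatment is not defined. Section 8.3 counts the days of an induction cycle from the start of chemotherapy and not of study drug. Section 13.2 staggers the first 6 patients by the start of induction 1. Section 5.8 has crenolanib starting on Day 9. Sections 1 and 8.2.1 add a 7-day window and call for a discussion with the sponsor if the start would fall later than Day 16.

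Three sections govern how a death becomes known:

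- **14.5, collection.** SAE collection starts with the first tablet: "If a patient experiences an SAE after signing informed consent, but prior to receiving study drug, the event will NOT be collected". The sentence goes on to except events that the investigator thinks a protocol procedure may have caused. Section 13.8 puts the same limit, with the same exception, on adverse events in the CRF.
- **14.5, timing.** The investigator, "within 24 hours of learning of the SAE or subject death, must notify the sponsor".
- **14.8.** All deaths during the study are reported, by three routes. Deaths not clearly due to progression, and deaths of unknown cause, go as SAEs within 24 hours. A death unequivocally due to progression "should be communicated to the study monitor at the next monitoring visit", is entered in the CRF and is not an SAE.

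**The concern.** An all-cause rule that can fire on one death works only if each death reaches the sponsor and the Protocol Safety Committee promptly, and if it is clear which deaths count. The text leaves three openings.

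1. A progression death has two deadlines: 24 hours in 14.5 and the next monitoring visit in 14.8.
2. A death after enrolment but before the first tablet is reportable under the opening of 14.8, yet falls in a period for which 14.5 and 13.8 switch off event collection. If the clock starts with chemotherapy, as 8.3 and 13.2 suggest, that period lies inside the 30 days.
3. Section 14.8 covers deaths during the study, but 13.9 takes a patient off study at the start of a new therapy. After study drug is stopped, Section 3.2 asks for survival information only at least every 6 months. A patient who moves to other treatment and dies before Day 60 has no clear prompt route into the count.

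At stake is enrolment: further patients could start treatment in a cohort that the rule would already have halted.

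**Working it through.** **1. The plan's thresholds reproduce.** For n patients and a stated rate t, find the smallest r with r/n above t. The last column shows what is observed if one of those deaths is unknown at the decision.

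| Look | Rate t | Smallest r | r/n | One death unknown |
|---|---|---|---|---|
| Day 30, n = 6 | 10% | 1 | 16.7% | 0/6 = 0%, no halt |
| Day 30, n = 12 | 10% | 2 | 16.7% | 1/12 = 8.3%, no halt |
| Day 60, n = 6 | 20% | 2 | 33.3% | 1/6 = 16.7%, no halt |
| Day 60, n = 12 | 20% | 3 | 25.0% | 2/12 = 16.7%, no halt |

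These are the counts in 13.2.1. All four are minimal, so one unknown death at the boundary reverses each decision.

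**2. The routes side by side.**

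| Death of an enrolled patient | 14.5 | 14.8 |
|---|---|---|
| After first tablet, not clearly progression | 24 hours | 24 hours, as an SAE |
| After first tablet, unequivocal progression | 24 hours, if the words on subject death are read alone | Next monitoring visit, not an SAE |
| Before first tablet | SAE not collected, unless possibly caused by a protocol procedure | Reported if it occurs during the study; no statement on this period |

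The first row agrees. The other two do not.

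**3. The possible delay.** The interval between monitoring visits is not given; Section 15 calls them periodic. Section 15.2 has site teleconferences about twice a month, so roughly two weeks apart. For the first 6, Section 13.2 allows no more than 3 patients within 30 days of starting induction 1. It states no such stagger for the second 6.

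**4. The pre-tablet window.** With crenolanib on Day 9 it is Days 1 to 8: 8/30 = 27% of the 30-day period and 8/60 = 13% of the 60-day period. With a Day 16 start it is Days 1 to 15: 15/30 = 50% and 15/60 = 25%.

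**5. A worst-case illustration.** Let p be true Day 30 mortality and f the share of those deaths not known at the decision. The documents do not give f. Taking it as 27% or 50% assumes that deaths are spread evenly over 30 days, that every patient is at risk from Day 1 and that no pre-tablet death is counted. A milder 10% is shown beside them. Then q = p(1 − f), and the chance of a halt in the first 6 is 1 − (1 − q)^6.

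| p | f = 0 | f = 10% | f = 8/30 | f = 15/30 |
|---|---|---|---|---|
| 20% | 0.738 | 0.696 | 0.614 | 0.469 |
| 10.3% | 0.479 | 0.442 | 0.376 | 0.272 |

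For example, with p = 0.20 and f = 8/30, q = 0.20 × 22/30 = 0.147 and 1 − 0.853^6 = 0.614. Over both Day 30 looks (1 or more of the first 6, otherwise 2 or more of the second 6), the chance at p = 20% is 0.83, 0.79, 0.70 and 0.53.

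**The case against.** The strongest reply is that limits on SAE collection are not limits on knowing about deaths. Section 14.8 requires all deaths during the study to be reported, and even progression deaths go into the CRF. Deaths are a listed safety outcome in 13.8, and overall survival is a secondary objective. Section 13.2.1 nowhere says that its count comes from SAE forms. Moving from 6 to 12 patients, and from 12 to 24, already requires that the Day 30 and Day 60 criteria are not met, so vital status must be known at those points. The stagger in the first 6, the twice-monthly calls and the safety meetings (at least every six months or for every 6 patients per cohort) shorten any delay further. The slow route applies only to unequivocal progression.

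Most of this stands. A reader might infer that deaths before the first tablet will be missed and that the rule's chance of halting really drops to 0.47. The documents do not support that, because it needs every pre-tablet death to go uncounted, contrary to 14.8. It also needs every patient to be at risk from Day 1, whereas the induction schedule in Appendix IV foresees screening during induction chemotherapy, so some patients may enrol part-way through. A reader might also infer that the observed rate would be biased low against the 7.9% and 10.3% benchmarks. That depends on how the cited studies started their clocks, which the protocol does not say.

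If study treatment meant crenolanib alone, the pre-tablet gap would not touch the rule. Sections 8.3 and 13.2 argue against that reading, and the conflict over progression deaths remains either way. The checks at 6 and 12 patients do not help within a group of six, where enrolment can go on before a late death is known. The calls are not a duty to report deaths.

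**Conclusion.** The concern holds as an unreconciled conflict between 13.2.1, 13.8, 14.5 and 14.8, with an undefined clock, and not as evidence that deaths will be lost. Following 14.8 as written, a death that meets a one-death trigger can reach the sponsor at an unspecified later visit. For a death before the first tablet, a site could argue from 14.5 that nothing was due.

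What can be stated firmly is the sensitivity: one unknown death at the boundary reverses any of the four decisions. How often that would happen cannot be derived from the documents. The fall from 0.74 to 0.61 or 0.47 at 20% true mortality is an upper-end illustration under the assumptions listed; with 10% of deaths unknown it is 0.74 to 0.70. Reading the counts for the second group as cumulative is also an assumption. The repair is cheap and protects the trial's tightest safety rule, so it should be made.

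**What to change.** In 13.2.1, define the initiation of study treatment as Day 1 of induction 1, and state how patients enrolled part-way through induction are counted.

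Reconcile 13.8, 14.5 and 14.8 for the safety phase. Every death of an enrolled patient up to Day 60 from that date should be notified to the sponsor within 24 hours of the site learning of it, passed to the Protocol Safety Committee and counted in the rule. This should apply whatever the cause, whether or not crenolanib was started, and whether or not another therapy has begun. Progression deaths can still be classed as non-SAEs; only their notification needs to change.

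The cost is wording in four sections and a few more expedited notices. The thresholds and the treatment plan stay as they are.
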